This proposed research directly addresses these inter-related issues by investigating response to intensive semantically-oriented naming treatment for veterans with aphasia. Naming is the most common domain of impairment among persons with aphasia.^[18] First, the research seeks to identify neural, cognitive, and psycholinguistic factors that predict positive treatment response. It builds on promising results indicating that individuals with a range of language-impairment profiles may benefit from semantically-oriented naming treatment^[12, 19], and that cognitive function^[10] as well as degree of cortical and subcortical left-hemisphere damage may be predictive of naming treatment outcomes^[21]. Identifying factors that are prognostic of positive treatment response is critical for effective allocation of limited healthcare resources. Second, the research examines the dose-response relationship for naming therapy when delivered on an intensive schedule. An intensive schedule is widely argued to be important to maximizing treatment gains^[29, 30] and it is increasingly being adopted as a treatment delivery model^[5], with at least 11 organizations in North America currently offering intensive aphasia therapy programs. Defining the dose-response relationship for aphasia therapy is a critical first step in determining optimum dosage levels. Providing answers to these two interlocking questions – for whom is aphasia therapy effective, and how much of it is needed? – can set transformative new standards for how aphasia treatment is delivered within VHA.

A.1 Rehabilitation of communicative and naming impairments in aphasia

A.1.1. Stimulation of semantic representations relevant to naming: Semantic Feature Analysis

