Participants' performance on the set of cognitive measures identified above (section C.2.3) will be transformed into z-scores, to ensure that the scores may be compared across tasks. These transformed scores will be submitted to principal component analysis in order to identify one or more factors which account for performance across the measures. Based on previous findings^[10, 69], we anticipate that measures of executive function (WCST) and performance on the PPT will load on one factor, while measures of visuo-spatial memory (Rey Complex Figure) and other memory function (Camden Memory Test, topographical and word subtests) will load on a separate factor. Performance on tests of focused and divided attention (TEA) may also load on a separate factor.

These factors will be entered as predictors into separate linear regressions targeting primary and secondary dependent measures, to determine which cognitive factors predict these measures of treatment response. Based on previous results, we anticipate that the executive-function factor^[10, 71], the memory factor^[10, 66], and the attention measures^[10] will all be significant predictors of naming treatment response. If no reliable predictive relationships are found between these cognitive factors and treatment response, we will perform additional correlation analyses to examine the relationship between performance on individual cognitive tasks and treatment response. We may also subtract variance associated with aphasia severity (as assessed by the CAT mean language modality T-score) using stepwise linear regression, since different aphasia severities may be associated with different responses to treatment^[1]. Given that the studies referenced above have demonstrated the hypothesized relationships with sample sizes ranging from 7 to 33 participants, we expect that the present analyses will be sufficiently powered, given the proposed sample size of 50.

C.3.1.3 Voxel-based lesion symptom mapping (VLSM)

For each participant, lesion size and extent will be quantified and related to treatment response using voxel-based lesion symptom mapping (VLSM), to test the neuroanatomical hypotheses relevant to Specific Aim 1. These analyses will compare the structural MRI data collected for study participants with change scores based on their performance on outcome measures.

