We will use the MRICron program's nonparametric lesion mapping (NPM) feature to complete the lesion symptom correlations^[106]. These data will be structured such that there is a binary classification at the voxel level (i.e., ±lesion) and continuous behavioral data (change score associated with the different outcome measures: PNT scores and scores on acquisition/generalization probes). Since these data are likely not to satisfy parametric statistical assumptions, we will use the NPM program's Brunner-Munzel nonparametric test to relate behavioral performance on each of the treatment-outcome predictors (change scores) to lesion distributions^[107-109]. We will apply a cluster threshold of 10 contiguous voxels and threshold for a false discovery rate of .05 in order to control for type I error while maintaining sufficient power to detect effects. We will also include voxels that have at least a 25% lesion overlap across patients. VLSM analyses will focus on four principal regions of interest (ROIs): left anterior cortex, left posterior cortex, left basal ganglia, and left hippocampus. Previous work (reviewed in section B.2 above) has shown that positive response to aphasia treatment is associated with intact left hippocampus and left basal ganglia. In addition, some previous work suggests that negative treatment response is associated with more intact left anterior cortex^[21], but other work suggests that greater recruitment of left anterior cortex is associated with positive treatment response^[23]. Additional work has also found that more intact left posterior cortex is associated with more positive treatment response^[23].

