Change scores from program entry to program exit and/or follow-up will be computed for primary and secondary study measures: weekly PNT scores and acquisition/generalization probes. These scores will be correlated with lesion extent using VLSM, with analysis focusing on the four ROIs identified above. These correlations will serve to test the hypotheses relevant to Specific Aim 1 above. As predicted by Hypothesis 1c and consistent with the preliminary findings from the PIRATE participants (see B.2.1 above), we anticipate that there will be a significant negative correlation between change scores and lesion extent in left basal ganglia and hippocampus. Greater damage to structures required for learning and memory function (hippocampus) and to structures which can control maladaptive activation of damaged left-hemisphere tissue (basal ganglia) will result in poorer treatment outcomes. Also as predicted by Hypothesis 1c and consistent with preliminary data by Parkinson and colleagues (see B.2.1), we anticipate that extent of left-anterior hemisphere lesion will be positively correlated with change scores. Greater damage to left anterior cortex will prompt greater recruitment of right hemisphere cortex or other non-lesioned left hemisphere cortex, resulting in more positive treatment outcomes^[20, 25]. Furthermore, we anticipate that extent of left posterior cortex will be associated with poorer treatment outcomes, given Fridriksson's findings^[23].

Additional exploratory analyses will be carried out to examine how these neuroanatomical factors predict performance for the different outcome measures. We anticipate that brain regions which are positively correlated with change scores for acquisition probes will not be positively correlated with change scores for generalization probes, given the behavioral^[9] and neuroimaging evidence^[20] that treatment response for treated and untreated items/behaviors leans on different cognitive and neural mechanisms. We do not have any a priori predictions regarding what brain regions may be correlated with change scores for generalization probes.

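### The voxel test takes no account of overall lesion size, so if size is related to gain, a regional finding in C.3.1.3 cannot be separated from it

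*Combined protocol and SAP*

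**What the plan says.** Section C.3.1.3 of the combined protocol and SAP starts from lesion tracings: "For each participant, lesion size and extent will be quantified and related to treatment response". The tracings are turned into normalised lesion masks. Each voxel is then coded as lesioned or not, and the plan uses the "Brunner-Munzel nonparametric test to relate behavioral performance on each of the treatment-outcome predictors (change scores) to lesion distributions". Voxels enter only with "at least a 25% lesion overlap across patients". Error control is a 10-voxel cluster rule and a "threshold for a false discovery rate of .05".

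Four regions are of interest. For two of them the plan expects that "there will be a significant negative correlation between change scores and lesion extent in left basal ganglia and hippocampus", explained by the role of the hippocampus in learning and of the basal ganglia in controlling maladaptive activation. Posterior damage is expected to go with poorer outcome. Anterior damage is expected to go with better outcome.

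C.3.1.3 names no covariate, residualising step or matching on lesion size. Its only fallback is a split by aphasia severity, used only if no significant correlation is found. The optional removal of severity variance by stepwise regression belongs to the cognitive analyses in C.3.1.2.

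**The concern.** A participant with a lesion at a given voxel will, on average, have a larger stroke than one without. If total lesion volume is itself related to naming gain, a two-group comparison at that voxel carries part of the volume effect even when the voxel does not matter.

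The consequence depends on the sign:
- If larger strokes gain less, the test leans towards negative findings everywhere. That favours the basal ganglia, hippocampal and posterior predictions and works against the anterior one.
- If larger strokes gain more, the three negative predictions can be hidden and the anterior one falsely supported.

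The neuroanatomical part of Aim 1 asks which structures matter. Without lesion size in the analysis, a significant cluster cannot answer that question, and neither can a null one.

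**Working it through.** **Inputs from the documents.** Imaging sample 40 (C.1: 50 minus 20%). Minimum lesioned per voxel 0.25 × 40 = 10 (C.3.1.3). Binary voxel status and a Brunner-Munzel test without covariates (C.3.1.3). Stated power 0.80 at r = 0.38 with n = 40 (C.3.1.3).

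**Assumed inputs, not in the documents.** The correlation of volume with gain, the latent correlation of volume with voxel status, and the number lesioned at a voxel beyond the minimum of 10.

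**Step 1: the plan's own figure.** Power = Φ(atanh(r)·√(n−3) − z). With r = 0.38 and n = 40, atanh(0.38)·√37 = 2.43.
- One-sided 0.05: Φ(2.43 − 1.645) = 0.785. Other methods give up to 0.818, so 0.80 reproduces.
- Two-sided 0.05: Φ(2.43 − 1.960) = 0.682. Other methods give up to 0.716, so 0.80 does not reproduce.

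The plan states neither alpha nor sidedness. This point does not dispute the figure; it serves as a yardstick.

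**Step 2: correlation induced by size alone.** With no regional effect, the correlation between regional damage and gain is r(volume, gain) × r(volume, region). At the strong end of the assumed range, in absolute value, 0.5 × 0.7 = 0.35, close to the 0.38 the study is powered for. It would be significant with probability 0.718 one-sided or 0.604 two-sided. At 0.3 × 0.5 = 0.15 the probabilities are 0.234 and 0.149.

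**Step 3: the planned test at one voxel, two-sided.** Simulation with N = 40, no direct voxel effect and at least 10 lesioned. Cells show the percentage with p < .05 in either direction at 25% / 40% lesion prevalence (nominal 5%).

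| Latent volume–voxel r | Volume–gain r = 0 | −0.3 | −0.5 |
|---|---|---|---|
| 0.3 | 6.4 / 4.9 | 8.2 / 7.4 | 10.2 / 11.9 |
| 0.5 | 5.7 / 6.0 | 10.4 / 11.4 | 21.8 / 23.1 |
| 0.7 | 5.4 / 5.2 | 18.2 / 17.8 | 42.4 / 41.5 |

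With volume as a covariate in a linear model, the rate is 4.0% to 5.6% across the −0.3 and −0.5 columns.

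**Step 4: false results in the negative direction only.** With 16 of 40 lesioned, volume–gain r of −0.3 to −0.5 and volume–voxel r of 0.5 to 0.7, a significant negative result appears in about 11% to 41% of trials (nominal 2.5%), and in about 2% to 3% with volume in the model. At a weaker volume–gain r of −0.2, the unadjusted rate is 4.5% to 11% for volume–voxel r of 0.3 to 0.7. With no volume effect it is about 2.5%.

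**Step 5: do FDR and clustering remove it?** They limit chance findings. A confounded association is not a chance finding. Two rough simulated maps, whose layout and between-voxel correlation are also assumed, illustrate this:
- Four regions of 15 voxels, FDR .05, at least 10 significant voxels required in a region. At least one of the three regions was falsely negative in 0% of trials with no volume effect, 3% at −0.3/0.5, 17% at −0.4/0.7 and 36% at −0.5/0.7.
- Four regions of 30 voxels, FDR, at least 3 significant voxels required. The corresponding rate was 16% to 55% over the assumed range.

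The figures depend strongly on the cluster rule. The thresholds reduce the problem in mild settings and do not remove it in stronger ones.

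**The case against.** **The direction is not established.** A reader might infer that the protocol itself concedes that bigger strokes respond less, since section A says that "degree of cortical and subcortical left-hemisphere damage may be predictive of naming treatment outcomes". The documents do not support that reading. The sentence rests on a lesion-and-treatment study of 15 patients that sections A.2.2 and B describe as regional and mixed in sign: more anterior damage with better gains, more basal ganglia damage with worse. Section B goes on to link greater left-hemisphere involvement to better response. The sign of any overall size effect is therefore unknown. This objection stands, and the point has to cover both directions.

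**One size effect would not readily confirm the whole pattern.** A reader might also infer that a single non-specific effect could confirm three of the four predictions. A negative size effect would also push the anterior region negative, against its prediction. In the second simulated map, all three regions were falsely negative in 1% to 24% of trials, but all three without a negative anterior result in only about 0.3% to 4%. The full predicted pattern is thus a partial safeguard. It does not protect a claim about one region taken alone.

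**The rates are assumption-driven.** The 11% to 41% is for one voxel before FDR and clustering, with assumed correlations. The adjusted model also performs well partly by construction, because it adjusts for the same error-free linear volume that generated the gains. Both remarks stand.

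**Adjustment can go too far.** Total volume includes the region's own damage, so adjusting for it can remove a real effect of a large region. The plan chose a rank test because it doubted parametric assumptions, and the 15-patient study controlled for the other region's extent, not total volume. This argues against making an adjusted p-value the sole criterion. It does not argue for omitting lesion size. That study did account for other damage, and the planned test does not.

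**Conclusion.** The concern holds as a conditional one. C.3.1.3 specifies a test without lesion size and interprets its results as effects of particular structures. If volume is related to gain in either direction, following the plan exactly can credit a general size effect to a region or hide a real regional effect.

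The documents do not give the sign or strength of that relation. The 11% to 41% illustrates the negative direction for a single uncorrected voxel under the stated assumptions. It is not a forecast of the error rate of the final map, and with no relation there is no bias. The case for change rests on the design: the plan has no step that could tell the two explanations apart, and its severity split runs only after a null result.

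**What to change.** Compute total lesion volume from the normalised masks. The plan quantifies lesion size but does not name total volume as a variable; it follows from the masks without new data. Keep the planned Brunner-Munzel map and pre-specify beside it a volume-adjusted analysis of each of the four regional predictions, for example:
- a voxelwise or regional model of change score on lesion status or extent plus log lesion volume, with permutation p-values, since the rank test has no covariate term;
- for regional extent, optionally the volume outside the region, so that the region's own damage is not adjusted away.

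Report both analyses. Describe an association as region-specific only where the adjusted estimate keeps its direction and is not materially reduced, and state beforehand what counts as material. Otherwise report that it cannot be separated from lesion size.

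The cost is analysis wording and one covariate. If the regional partial correlation stayed at 0.38, power would fall from 0.785 to Φ(atanh(0.38)·√36 − 1.645) = 0.775 one-sided, or from 0.682 to 0.670 two-sided. The loss will be larger for regions such as anterior or posterior cortex where they make up much of the lesion volume, because the partial correlation itself will shrink.

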Given that behavioral therapy for chronic aphasia is efficacious but resource-intensive, it is critical to identify factors that will be predictive of who is most likely to benefit from such therapy. Studies examining the role of cognitive factors in aphasia therapy provide evidence that a broad range of factors relevant to learning may be predictive of treatment response. Executive function, visuospatial memory, and attention (both divided and focused) have all been found to predict naming treatment outcomes. However, it is unclear whether these factors are more or less strongly predictive of outcomes for psycholinguistically-motivated naming treatments like SFA than for the cueing hierarchies used in previous studies. It is also unknown whether these cognitive factors are predictive of acquisition of trained behaviors, generalization (stimulus or response), or both.

Studies regarding potential neuroanatomical predictors of treatment response provide similarly encouraging but limited evidence for the potential prognostic role of neurological findings for aphasia therapy outcomes. Further research is required to determine the prognostic value of the extent of left-hemisphere lesion (and corresponding recruitment of right-hemisphere homologues) in forecasting likely treatment response. Further research is also required to determine whether neuroanatomical predictors are prognostic only of skills/items treated in therapy, or whether they are also prognostic of generalization to untreated items and to improvements in broader, standardized measures of naming and language function.

A.3 Dosage levels and treatment response in aphasia

There is abundant evidence for the efficacy of behavioral rehabilitation strategies rooted in cognitive neuropsychology and psycholinguistics for improving the language function of adults with aphasia^[1, 2], including naming treatments like those described above. Moreover, the literature also suggests that providing more treatment results in greater improvement in language function^[1, 6, 7, 78, 79]. However, these findings are preliminary, because the total amount of treatment has often been confounded with intensity of treatment. Research is therefore needed to address the effects of treatment amount independent of treatment intensity. Systematically examining the connection between the amount of treatment and the resulting gains is critical for the ultimate goal of identifying optimum dosages for aphasia therapy.

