Some participants may also have co-occurring conditions which would prevent them from participation in the imaging arm of the study (claustrophobia; presence of metal in the body). These participants will be enrolled in the study but will not complete imaging procedures. A chart review of PIRATE participants to date indicates that approximately 20% of veterans enrolled in PIRATE may have such exclusionary criteria: roughly 17% report pacemaker or other implanted metal objects or devices incompatible with MR scanning. Thus, the participant sample used to address the neuroanatomical hypotheses proposed under Specific Aim 1 may be smaller than the sample contributing data the other proposed analyses. Under the worst case scenario of no overlap between these imaging-related exclusionary criteria and those described in the preceding paragraph, we expect to obtain a sample size of 40 participants (50 minus 20%) to conduct the proposed imaging-related analyses. As described in section C.3.1.3 below, this sample size should be sufficient to detect the relationships relevant to the neuroanatomical hypotheses.

C.2 Procedures

The schedule of procedures for participants enrolling in the study is summarized in the flowchart in Figure 4. Participants enrolling in the research study will receive a single pre-treatment structural MRI and a battery of cognitive assessments at program entry (see section C.2.3 below). They will also have their performance on standardized measures of naming and other language functions assessed repeatedly throughout the protocol (see section C.2.2 below), and they will receive an intensive dose of a treatment (SFA) designed to target lexical-semantic processes (see section C.2.1 below). Participants' performance on treated and untreated lexical items will be probed three times weekly, to assess acquisition and generalization and to decide when participants will move to a novel set of treatment exemplars.

Half the participants will be randomly assigned to a delayed-treatment condition. The purpose of this condition is to provide an additional measure of experimental control, to ensure that any observed improvements are not due simply to the social contact afforded by the residential component of the treatment program. Previous work [7] has found that simple exposure or engagement in the absence of specific therapy

[figure not shown]

Figure 4: Testing and treatment procedures for study participants

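### The predicted split between predictors of acquisition and of generalization has no test of the difference behind it, so a result significant for one outcome only could be read as a dissociation

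*Combined protocol and SAP*

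**What the plan says.** Section C.3.1 makes gain on treated items the primary dependent variable for Aim 1. Gains on related untreated items and on the Philadelphia Naming Test are secondary.

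Cognitive factors (C.3.1.2): "These factors will be entered as predictors into separate linear regressions targeting primary and secondary dependent measures". The section expects the executive, memory and attention measures all to predict naming response. It predicts no contrast between outcomes.

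Lesions (C.3.1.3): a nonparametric test is used "to relate behavioral performance on each of the treatment-outcome predictors (change scores) to lesion distributions", with a ten-voxel cluster requirement and a "threshold for a false discovery rate of .05". The analysis concentrates on four regions of interest. The comparison of outcomes is introduced as follows: "Additional exploratory analyses will be carried out to examine how these neuroanatomical factors predict performance for the different outcome measures". The prediction then is that "brain regions which are positively correlated with change scores for acquisition probes will not be positively correlated with change scores for generalization probes". The reason given is earlier evidence that "treatment response for treated and untreated items/behaviors leans on different cognitive and neural mechanisms".

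Background (A.2.3): "It is also unknown whether these cognitive factors are predictive of acquisition of trained behaviors, generalization (stimulus or response), or both".

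No section plans a predictor-by-outcome interaction, a comparison of dependent correlations or an interval for a difference. The multivariate model in C.3.2 concerns trends over time, not predictors.

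**The concern.** The prediction pairs an association that is present with one that is absent. Absence cannot be shown by a non-significant test, and a difference cannot be shown by two tests falling on opposite sides of 0.05. With no comparison planned, a non-significant generalization result is the only thing that could be taken as confirmation.

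The background already reads evidence in this way. Section A.2.2 describes a study of 10 patients in which hippocampal measures correlated with gains on treated items but not on untreated items, and it takes the relationship to be confined to treated items.

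At stake is a claim that acquisition and generalization rest on different brain regions when one shared association would explain the data. The design can address the question directly, because both gains are measured in the same people.

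**Working it through.** **Inputs from the documents.** n=40 for imaging (C.1) and n=50 for the cognitive analyses (C.3.1.2). Stated power is 0.80 at r=0.38 with n=40. The planning correlations are 0.65 to 0.85, and the true ones are expected to be somewhat weaker (both C.3.1.3).

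**Inputs assumed.** The correlation between the two gains is 0.4, with 0.3 to 0.7 as a range. The reliability of generalization gains relative to acquisition gains is 1, or 0.5 to 0.7. The documents give neither.

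**The plan's own figure.** Power = Φ(atanh(r)·√(n−3) − z). With r=0.38 and n=40, atanh(0.38)·√37 = 0.400 × 6.083 = 2.43.
- One-sided 0.05: Φ(2.43 − 1.645) = 0.785. Two variants of the formula give 0.79 and 0.82, so the stated 0.80 reproduces.
- Two-sided 0.05: Φ(2.43 − 1.96) = 0.68. The variants give 0.69 and 0.72.

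**One illustration (n=40).** The critical correlation at two-sided 0.05 is 2.024/√(38 + 2.024²) = 0.312. Suppose the observed correlations are 0.40 with acquisition and 0.28 with generalization, and the gains correlate 0.4. The first is significant and the second is not. The Williams test for dependent correlations, with 37 df, is

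t = (rA − rG)·√{(n−1)(1+rAG) / [2·D·(n−1)/(n−3) + m²(1−rAG)³]},

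where m is the mean of rA and rG.
- D = 1 − 0.1600 − 0.0784 − 0.1600 + 2(0.40)(0.28)(0.40) = 0.6912.
- t = 0.12·√(54.6/1.482) = 0.73, p about 0.47.

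The pattern that would look like a dissociation carries almost no evidence of a difference.

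**How often this arises.** Simulation of a predictor and two gains (trivariate normal), with the same true association to both. Lower reliability enters as rG = r·√reliability; for example, 0.40·√0.5 = 0.28. Each correlation is tested at two-sided 0.05.

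| True r | Relative reliability | n | Significant for acquisition only |
|---|---|---|---|
| 0.38–0.40 | 1 | 40 | 15–17% |
| 0.38–0.40 | 1 | 50 | 11–14% |
| 0.38–0.40 | 0.5–0.7 | 40 or 50 | about 25–39% |
| 0.65 | 1 | 40 or 50 | below 1% |
| 0.65 | 0.5–0.7 | 40 | 4–13% |

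A rough check for the first row: if the two tests were independent, with power 0.69 each, the rate would be 0.69 × 0.31 = 21%. Correlation between the gains lowers it.

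Sensitivity at r=0.38, n=40, equal reliability: with gains correlated 0.3, 0.5 and 0.7, the rate is 18%, 15% and 12% two-sided, and 14%, 12% and 9% at one-sided 0.05.

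**The direct comparison in the same settings (r=0.38–0.40).** Comparing dependent correlations, or standardized gains, wrongly favours acquisition in 1–3% of trials with equal reliability and 4–11% with reliability 0.5–0.7. A comparison of raw gains is not safe: if generalization gains have half the spread of acquisition gains (assumed), it wrongly favours acquisition in 25–47%.

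**Power of the direct test.** For true correlations of 0.38 and 0 at n=40, it is 0.55 to 0.71 with the gains correlated 0.3 to 0.5.

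**The case against.** The strongest reply is that the plan commits to no faulty inference. It writes no rule for declaring a dissociation, it labels the lesion comparison exploratory, and it holds no prior view on which regions relate to generalization. The wording about distinct mechanisms gives the reason for the prediction, taken from earlier studies; it is not a conclusion to be drawn from this trial's pattern. All of this stands. A reader might infer that the protocol judges the question by significance in one outcome and not the other, but the documents do not say so. What remains is that nothing else in the plan could bear on the prediction.

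A reader might also extend the point to the cognitive factors as a planned contrast. C.3.1.2 predicts none, and separate regressions per outcome are routine. The caution applies there only if those regressions are used to answer the open question in A.2.3.

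A third stronger reading is that generalization gains are known to be less reliable, so that false splits would be frequent. The documents give no reliability for either gain, and the treated and related sets have 40 items each. The 25–39% range is therefore conditional, and 11–17% is the figure without that assumption. With correlations as strong as the planning values and equal reliability, the problem almost disappears. C.3.1.3 itself, however, expects weaker ones.

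Finally, the calculation uses single correlations. The planned voxelwise tests with false-discovery control are stricter, so power per test is probably lower than modelled.

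**Conclusion.** The point holds as a gap in the analysis plan: a predicted difference between two associations has no test of that difference. One shared association of about the size the plan says it can detect would produce significance for acquisition alone in about 11–17% of trials with equal reliability, and in about 25–39% if generalization gains are markedly less reliable. Both ranges rest on the assumed correlation of 0.4 between gains, and the second also on the assumed reliability. The rate is below 1% at r=0.65 with equal reliability.

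The documents do not support saying that the plan has adopted a significance-in-one-only rule, or that it predicts a dissociation for cognitive factors. The exploratory label limits the weight of the lesion comparison but does not make the inference valid. The change is worth making because it needs no new data.

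**What to change.** For the four regions of interest, add a direct within-person comparison of the two associations on a standardized scale. This can be a test of two dependent correlations, or a predictor-by-item-type interaction on standardized gains, reported with its confidence interval. Do the same for the cognitive factors if any contrast between outcomes is to be claimed. State that different predictors will be claimed only from this test, and that significance for one outcome alone will not be described as a dissociation.

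Do not base the test on raw gain differences, because unequal spread alone can create a false difference. Report the reliability of both gain scores, with a sensitivity analysis corrected for unreliability, since standardizing does not remove that source of error.

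The cost is a paragraph of analysis-plan wording and one added model per predictor set. The downside is the modest power shown above: some true dissociations will be reported as unresolved.
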